**Coronary ARteriogenesis with combined Heparin and
EXercise therapy in chronic refractory Angina (CARHEXA):
A phase 3 double-blind, placebo-controlled, parallel group
study**

December 25, 2012

ABSTRACT

Background: Although experimental studies on the stimulation of coronary arteriogenesis have been promising, not a single drug has been proved to be applicable in clinical practice, either due to lack of efficacy or because of undesired side effects. Encouraging results have been obtained with combination of heparin (H) coupled with a stress inducing ischemia and augmenting shear stress, such as exercise.

Aim: to establish the coronary arteriogenetic efficacy of H combined with exercise in patients with intractable coronary artery disease.

Methods: We will recruit 60 "no-option" patients with chronic stable angina refractory to optimal medical management, and not suitable for percutaneous and/or surgical revascularization therapy. As further inclusion criteria eligible patients are able to exercise (and enter a cardiac rehabilitation program). In a prospective, randomized, double-blind study design these "no-option" patients will be allocated (30 for each of the 2 groups) to one of 2 treatment groups: 1) standard physical rehabilitation (i.v. placebo 10 min prior to each of 2 exercise session per day for 5 days a week for 2 weeks); 2) drug-primed physical rehabilitation (same modality as 1, but with H, 100 UI/Kg up to a maximum of 5.000 IU iv, 10 min prior to the exercise). All patients will undergo exercise stress echo (with wall motion score index, coronary flow reserve on left anterior descending and global longitudinal strain evaluation) and cardiac CT (with coronary collateral assessment) both before and after the therapy cycle.

Endpoints. Clinical and imaging (by blinded observers) assessment will be performed before and after treatment. **Primary clinical endpoint** is Canadian Cardiovascular Society (CCS) angina severity, ranging from class 1 (mild) to 4 (severe). **Secondary stress imaging functional endpoint** is peak Wall Motion Score Index (WMSI) at stress echo (ancillary endpoints: global longitudinal strain and coronary flow reserve). **Tertiary imaging endpoint** is Coronary Collateral Circulation Score at cardiac CT.

Epidemiological and clinical background

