Our approach is based on the combination of pharmacological stimuli (with heparin) on top of a 2-week cycle of physical rehabilitation (in patients capable to exercise). The rationale for this chemical-physical cocktail stems from the fact that increase in shear stress (achieved with exercise), or heparin – when used alone - have no significant coronary arteriogenic effect, which is consistently present, and clinically significant, when the two stimuli are coupled (*Fujita M et al. 1988*). The basic principle of heparin treatment is potentiation of angiogenic growth factors, which

are overexpressed by increased shear stress at the site of pre-existing collateral vessels as a result of exercise or pacing. Although the precise mechanisms by which heparin potentiates arteriogenesis remain to be completely elucidated, heparin administration combined with exercise (*Tateno S et al 2001*) has great potential in treating patients with effort angina who are not indicated for conventional reperfusion therapy.

Study hypothesis

In the large and expanding population of "no-option" patients with refractory angina, a clinically significant coronary arteriogenic effect can be obtained through a combination of pharmacological (heparin) and physical (rehabilitation exercise program) stimuli, when used in combination.

Overall study design

We will recruit 60 patients with chronic stable angina refractory to medical management, and not suitable for percutaneous and/or surgical revascularization therapy. As additional criterion for treatment eligibility, patients will have exercise capacity allowing to enter a rehabilitation program. In a prospective, randomized, open-label study design these "no-option" patients will be allocated (30 for each group) to 2 treatments: 1) standard physical rehabilitation (2 exercise session per day for 5 days a week for 2 weeks); 2) drug-primed physical rehabilitation (same modality as 1, but with H, 100 UI/Kg up to a maximum of 5.000 IU iv, 10 min prior to the exercise). All patients will undergo exercise stress echo (with wall motion score index, coronary flow reserve on left anterior descending and global longitudinal strain evaluation) and cardiac CT (with coronary collateral assessment) both before and after then therapy cycle.

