Inclusion criteria: patients with documented coronary artery disease not amenable of further treatment and belonging to the "no-option" category (see above definition), with symptoms consistent with angina pectoris.

Exclusion criteria: patients with unstable angina, recent acute myocardial infarction, uncontrolled hypertension, haemodynamically significant valvular heart disease, bronchial asthma and neurologic and/or orthopedic illnesses that limit exercise capacity will be excluded. Patients receiving vitamin K antagonist will be excluded. Patients should not be actively involved in programmes of cardiac rehabilitation or exercise training.

All medications will remain unaltered during the study

Clinical and imaging (by blinded observers) assessment will be performed before and after treatment. **Primary clinical endpoint** is Canadian Cardiovascular Society (CCS) angina severity, ranging from class 1 (mild) to 4 (severe). **Secondary stress imaging functional endpoint** is peak Wall Motion Score Index (WMSI) at stress echo (ancillary endpoints: global longitudinal strain and coronary flow reserve). **Tertiary imaging endpoint** is Coronary Collateral Circulation Score at cardiac CT.

Detailed Work Plan

The overall architecture of the project is structured into work-packages (WP) that will be run by separate teams, in parallel with each other:

WP0- Study design and statistical plan

WP1- Patient recruitment and treatment

WP2-Assessment of treatment effect on inducible ischemia by stress echo

WP3- Assessment of Coronary Collateral Circulation by MDCT

WP0- Study design and Statistical plan

Sample size calculation. The study is sized to detect with 80% power a clinically significant difference in the chosen endpoints with $\alpha=0.05$. For primary endpoint, a Canadian Class Angina = 2.5, with 0.5 standard deviation, and with an expected, clinically significant improvement of 0.5 will lead to a sample size of 16 patients per arm (94 % power with 25 patients per arm). For secondary endpoint, a peak WMSI = 1.4, with 0.25 standard deviation, and with an expected, clinically significant improvement of 0.2 will lead to a sample size of 25 patients per arm. Overall a drop-out rate of 20 % is expected, and therefore 60 patients will be initially considered and 50 are expected to complete the trial (25 for each arm)

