Statistical plan: All continuous data will be given as mean+ SD. Baseline characteristics between the groups will be analyzed by Student t test for continuous data and chi-square/Fisher exact test for categorical data. Outcomes at follow-up examinations will be analyzed with chi-square test (for angina class) and paired Student t test (for approximately normally distributed data such as Wall Motion score index). Differences are considered statistically significant at a 2-sided P value of

<0.05. Electronic Case Report form preparation, ad interim and final data analysis will be performed by the Biometry Unit of the Institute of Clinical Physiology.

Core lab reading: All imaging data will be read by a single reader blinded to patient identity and study conditions.

Expected results: The group treated with active drug therapy will show a significant improvement of clinical, functional and perfusion indices when compared to standard rehabilitation therapy

WP1- Patient recruitment and treatment

CARHEXA is a prospective, randomized, single-center study: clinical enrollment and data collection will be done by Belgrade Unit. The Belgrade center has a recent tradition of clinical and scientific excellence in the field of diagnosis and treatment of coronary artery disease and has the facilities required to complete the study.

Ethical Committee submission will be presented at local authority by the Belgrade Unit, also responsible of clinical enrollment and data collection. We will recruit 60 patients with chronic stable angina refractory to medical management and not suitable for percutaneous and/or surgical revascularization therapy (see the above definition of “no-option” patients). In a prospective, randomized, open-label study design these "no-option" patients will be allocated (30 for each of the 2 groups) to one of 2 treatment groups: 1) standard physical rehabilitation (2 exercise session per day for 5 days a week for 2 weeks) with placebo (iv saline 10 min prior to exercise) ; 2) drug-primed physical rehabilitation (same modality as 1, but with H, 100 UI/Kg up to a maximum of 5.000 IU iv, 10 min prior to the exercise).

The Canadian Cardiovascular Society (CCS) classification of angina severity, ranging from class 1 (mild) to class 4 (severe), is used routinely in patients with coronary artery disease and is a recognized marker for disease progression.

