The SAQ is a 19- item questionnaire that measures 5 clinically important dimensions of health in patients with CAD: angina frequency, angina stability, physical limitations, treatment satisfaction, and disease perception/QOL. Each domain has a score ranging from 0 to 100, with higher scores indicating less disease burden. The quality of life assessed with SAQ has been shown to correlate with long-term survival and hospitalization for acute coronary syndrome among patients with chronic CAD (*Spertus JA et al, Circulation 2002*).

Intravenous injections will be given by a study nurse not involved in the process of data acquisition and analysis.

WP2: Assessment of treatment effect on inducible ischemia by Stress Echo

Background: Stress echocardiography is an established technique for the diagnostic and prognostic evaluation of coronary artery disease. Wall motion score index assesses in a semi-quantitative way the extent of inducible ischemia, which is related to the anatomic and prognostic severity of underlying coronary artery disease. Noninvasive external pacing has the same accuracy as other physical and pharmacological stressors, and can be the first-choice option in patients with permanent pacemaker (Sicari *et al.* 2009).

Methods: All patients will undergo a resting echo and a stress echo, with either heparinized exercise (Group 1) or exercise (Group 2), according to standard clinical protocol (Sicari *R et al, Eur Heart J* 2009). Resting echo will assess all left ventricular function and remodeling indices, as previously described (Bolognese L *et al, Circulation* 2004). No change in underlying optimal conventional medical therapy will be done, except for clinically driven reasons, during the study period. Wall Motion Score Index (each segment from 1=normal to 4=dyskinetic in a 17 segment model of left ventricle) will be calculated at baseline and peak stress following the standard protocols of European Association of Echocardiography. In all patients a quantitative assessment of longitudinal strain by 2D speckle tracking will be performed.

WP3: Assessment of Coronary Collateral Circulation by MDCT

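### WP2 wording leaves open whether both arms have the stress echo under the same condition, and should be reconciled with the rest of the protocol

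*Combined protocol and SAP*

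**What the plan says.** WP2 Methods states that each participant "will undergo a resting echo and a stress echo, with either heparinized exercise (Group 1) or exercise (Group 2), according to standard clinical protocol". No other section describes how the test is carried out.

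The Abstract and Overall study design describe the test without reference to arm: "All patients will undergo exercise stress echo (with wall motion score index, coronary flow reserve on left anterior descending and global longitudinal strain evaluation". In Overall study design the same sentence goes on "and cardiac CT (with coronary collateral assessment) both before and after then therapy cycle", so the test is done at two visits.

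Injections are described elsewhere as part of treatment. In the Abstract the control arm receives "i.v. placebo 10 min prior to each of 2 exercise session per day for 5 days a week for 2 weeks", and the drug arm receives heparin on the same pattern. Overall study design and WP1 also place heparin shortly before the rehabilitation exercise.

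Peak WMSI is the secondary endpoint, with strain and coronary flow reserve ancillary to it. WP0 sizes the trial on it as well as on CCS class: "For secondary endpoint, a peak WMSI = 1.4, with 0.25 standard deviation, and with an expected, clinically significant improvement of 0.2". For analysis, WP0 names a "paired Student t test (for approximately normally distributed data such as Wall Motion score index". On reading, WP0 states: "All imaging data will be read by a single reader blinded to patient identity and study conditions".

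**The concern.** Grammatically, the phrase about heparin qualifies the stress echo, and it sits where a reader would look for the test condition. The Detailed Work Plan has the work packages run by separate teams in parallel, so a stress-echo team working from its own section could follow it as written. The arms would then be tested under different conditions, and no placebo is named for the test.

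This would matter for one comparison. WP0 expects that "The group treated with active drug therapy will show a significant improvement of clinical, functional and perfusion indices when compared to standard rehabilitation therapy". For the functional indices, a difference between arms reflects new collateral vessels only if both arms are tested alike. If heparin has any immediate effect on wall motion, strain or flow reserve during exercise, a follow-up difference would contain that effect as well as the effect of the two-week cycle. A blinded reader protects the scoring of the images but cannot undo a difference in how they were acquired. With no placebo at the test, the procedure could also reveal the arm to those performing it.

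**Working it through.** **1. The plan's own figure.** Inputs from WP0, Sample size calculation: difference 0.2, SD 0.25, alpha 0.05, power 80%. WP0, Statistical plan, makes the test two-sided.

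n per arm = 2 × (1.960 + 0.842)² × 0.25² / 0.2² = 2 × 7.85 × 1.5625 = 24.5, so 25. Power with 25 per arm is 80.7% by the normal approximation. The stated 25 is reproduced, and nothing in it depends on the test condition.

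**2. The sections side by side.**

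| Section | Test condition | Where heparin is given |
|---|---|---|
| Abstract | exercise stress echo, all patients, before and after | before rehabilitation exercise |
| Overall study design | same | before rehabilitation exercise |
| WP1 | not described | before rehabilitation exercise |
| WP2 Methods | heparinized exercise or exercise, by group | not separately stated |

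The first two rows do not say whether anything is injected at a test visit. They therefore do not flatly contradict WP2, but they do not resolve it either. WP2 also calls the heparin arm Group 1, whereas the other three sections list it second. No analysis or allocation text uses the number, so that is editorial.

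**3. What each reading does to the WMSI comparison.** Let δ be the true between-arm difference at follow-up and b a constant shift in WMSI caused by heparin at the test. Randomization makes the expected baseline difference zero when no heparin is given at baseline.

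- Arm label only: the follow-up comparison estimates δ, and so does the comparison of change.
- Literal text, heparin at both visits in one arm: the follow-up comparison estimates δ + b. The comparison of change estimates (δ + b) − b = δ.

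The literal reading therefore harms a comparison of follow-up values but not a comparison of change, provided the shift is the same at both visits. WP0 names only a paired test for WMSI and fixes no between-arm test, so the plan does not tell us which comparison would be made.

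**4. Illustration of size.** The document gives no value for b, so b is assumed. Setting: two-sample t test on follow-up values, no true effect, 25 per arm, SD 0.25, 48 degrees of freedom.

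Standard error = 0.25 × √(2/25) = 0.0707. Noncentrality = b / 0.0707.

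| Assumed b | Noncentrality | Rate of p < 0.05 |
|---|---|---|
| 0 | 0 | 5% |
| 0.02 | 0.28 | 5.9% |
| 0.05 | 0.71 | 10.7% |
| 0.059 (one grade in one of 17 segments, 1/17) | 0.83 | 12.9% |
| 0.10 | 1.41 | 28.3% |

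If the shift worked against a true difference of 0.2, the expected difference would be 0.15 or 0.10 for b = 0.05 or 0.10. Power by the normal approximation would fall from 80.7% to 56.4% or 29.3%.

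**The case against.** The strongest reply is that the phrase merely names the two treatment arms. Much supports this. The sentence itself goes on to invoke the standard clinical protocol, and WMSI is to follow the European standard methods. Everywhere else heparin belongs to rehabilitation. No dose, timing or placebo is given for a test visit. Taken literally, the sentence would put study drug into a test done before therapy starts. WP1 assigns injections to a nurse who takes no part in data acquisition, which fits injections being a treatment activity. All of this stands and makes the label reading plausible. It does not close the matter, because no section says that a label is meant or that both arms are tested alike.

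A second reply is that an exercise test with heparin is still an exercise test, so the sections are not strictly contradictory. That is right. This is an unresolved inconsistency, not two opposed instructions.

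A third reply is that a constant shift at both visits cancels from change. That is also right, as the working shows. It helps only if change is what is compared between arms, and the plan does not say so.

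A reader might go further and infer that heparin will be given at the follow-up test in one arm only, so that even an analysis of change is biased. Under that scenario, with within-patient correlations of 0 to 0.7, false-positive rates would be about 8–15% for a shift of 0.05 and 17–43% for 0.10. The document does not support this. The WP2 sentence makes no distinction between visits, and no other section describes heparin at follow-up alone.

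**Conclusion.** The point holds as an internal-consistency matter of minor to moderate weight. WP2 Methods, as worded, lets the stress-echo condition differ by arm, and nothing elsewhere rules that out.

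The consequence is conditional on three things: the sentence is followed literally, heparin has some immediate effect on the measurements, and follow-up values are compared. The rates of 5.9% to 28.3% depend on assumed shifts of 0.02 to 0.10 and are illustration only; 0.10 is already half the planned effect of 0.2. If the phrase is an arm label, the rate stays at 5% and only the wording changes.

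It would be wrong to conclude that the secondary endpoint is biased, or that the sponsor intends heparin at the test; the document establishes neither. The primary CCS endpoint, the CT collateral score and the stated sample sizes are untouched.

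**What to change.** Reconcile WP2 Methods with the Abstract, Overall study design and WP1. State in one sentence that baseline and follow-up stress echo are acquired under one identical condition in both arms, with the sponsor to state which condition. If the phrase was meant only to identify the treatment arms, say so and move it away from the description of the test. Align the group numbering in WP2 with the other sections at the same time.

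The cost is a one-sentence clarification, with no additional tests, patients or change to the sample size.

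### Peak WMSI also counts wall-motion abnormality present at rest, and the plan names no between-arm analysis that uses the resting WMSI it collects

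*Combined protocol and SAP*

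**What the plan says.** The endpoint paragraph under Overall study design says that the secondary endpoint "is peak Wall Motion Score Index (WMSI) at stress echo". WP2, whose title concerns the treatment effect on inducible ischemia, says in its Background: "Wall motion score index assesses in a semi-quantitative way the extent of inducible ischemia". WP2 Methods defines the score: "each segment from 1=normal to 4=dyskinetic in a 17 segment model of left ventricle) will be calculated at baseline and peak stress". I read baseline there as the resting stage of the stress test, because the same paragraph calls for a resting echo and a stress echo.

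The sizing in WP0 uses peak WMSI only: "a peak WMSI = 1.4, with 0.25 standard deviation", and an "expected, clinically significant improvement of 0.2 will lead to a sample size of 25 patients per arm". No expected resting WMSI appears anywhere.

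The Statistical plan in WP0 assigns WMSI to a paired Student t test. It defines no rest-to-peak difference and no covariate adjustment. The Expected results paragraph nevertheless anticipates better results on active drug than on standard rehabilitation, which is a between-arm statement.

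The exclusion criteria rule out recent acute myocardial infarction. They do not rule out old infarction or resting wall-motion abnormality, and entry does not require a positive stress echo.

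**The concern.** A segment that is akinetic from an old scar scores the same at rest and at peak. Peak WMSI is therefore the resting abnormality plus whatever stress adds, while WP2 interprets it as the second part alone. Three things follow.

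- **Interpretation.** A null result could mean no effect on ischemia, or that most of the score was fixed. A positive result could mean less ischemia or better resting function. The resting value would help to tell these apart, and no analysis uses it.
- **Precision.** If follow-up peak values are compared between arms without adjustment, differences in scar between patients add to the standard error. A chance imbalance in scar also shifts the observed difference in that particular trial.
- **Target.** The 0.2 improvement was set without reference to how much of the 1.4 is inducible.

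**Working it through.** **1. Reproducing the plan's figure.** Inputs from WP0: difference 0.2, SD 0.25, 80% power, two-sided 0.05.

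n per arm = 2 × (1.960 + 0.842)² × 0.25² / 0.2² = 24.5, so 25. Power at 25 per arm = Φ(0.2 / (0.25 × √(2/25)) − 1.960) = 80.7%. The t-based version gives 79.1%.

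The stated 25 reproduces. A one-sample paired calculation with the same inputs would need only 15 patients in total, so the sizing is a two-sample comparison using the between-patient SD of peak WMSI. That SD already contains resting variation.

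**2. What each analysis does with stable scar.** In a patient's pre-to-post change in peak WMSI, a fixed resting score cancels. It does not cancel when follow-up peak values are compared between arms. If a share s of the variance is stable resting abnormality, its SD is 0.25√s, and the standard error of its chance imbalance at 25 per arm is 0.25√s × √(2/25): 0.039 at s = 0.3 and 0.050 at s = 0.5, about 19% and 25% of the 0.2 target.

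**3. What resting WMSI adds to pre-treatment peak.** Assumptions, none from the protocol: s is 0.3 or 0.5; c is the pre-post correlation of the remaining part of the score; resting WMSI is read without error, which favours the concern.

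- Adjusting for pre-treatment peak: SD = 0.25 × √(1 − ρ²), with ρ = s + (1 − s)c.
- Adjusting for peak and rest: SD = 0.25 × √((1 − s)(1 − c²)).

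Power at 25 per arm for a difference of 0.2 (unadjusted 80.7%):

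| s | c | Peak only | Peak + rest | Added by rest (points) |
|---|---|---|---|---|
| 0.3 | 0 | 84.3% | 92.2% | 8.0 |
| 0.3 | 0.3 | 90.8% | 94.3% | 3.5 |
| 0.3 | 0.5 | 96.1% | 97.4% | 1.3 |
| 0.3 | 0.7 | 99.6% | 99.7% | 0.1 |
| 0.5 | 0 | 90.4% | 97.9% | 7.5 |
| 0.5 | 0.3 | 96.1% | 98.7% | 2.6 |
| 0.5 | 0.5 | 99.0% | 99.6% | 0.6 |

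With any moderate pre-post correlation, pre-treatment peak does most of the work.

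**4. Cost of subtracting rest.** Suppose each reading has error SD m (assumed) and the true score is otherwise stable. The change in peak then has SD m√2; the change in (peak − rest) uses four readings and has SD 2m. In simulation at 25 per arm, power for the two was about 90% and 64% at m = 0.15, about 100% and 93% at m = 0.10, and about 100% for both at m = 0.05.

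**5. The 0.2 target against an assumed resting score.** Over 17 segments, a mean peak of 1.4 is (1.4 − 1) × 17 = 6.8 points above normal, and 0.2 is 0.2 × 17 = 3.4 points. If the mean resting WMSI is r and treatment acts only on the inducible part, the largest possible fall is 1.4 − r, and the share that must disappear is 0.2 / (1.4 − r).

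| Assumed r | Largest fall | Share needed for 0.2 |
|---|---|---|
| 1.00 | 0.40 | 50% |
| 1.10 | 0.30 | 67% |
| 1.20 | 0.20 | 100% |
| 1.25 | 0.15 | not reachable |

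Any gain in the placebo arm would reduce the between-arm difference further.

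**The case against.** The strongest reply is that the plan names a paired test and images every patient before and after treatment. On that reading stable scar cancels, so the noise and imbalance arguments fall away. That is correct for the within-patient change. It does not settle the matter, because a paired test within each arm gives no heparin-versus-placebo comparison, which is what the sizing and the expected results call for.

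A reader might infer that adjusting for resting WMSI lifts power from 81% to 92% or 98%. Those figures set resting WMSI against no baseline adjustment at all. Pre-treatment peak already carries the scar, so the proper measure is the last column of the table in step 3.

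A reader might also infer that the 0.2 target is out of reach. The protocol gives no resting WMSI, so it does not support that. The ceiling also assumes that treatment leaves resting function unchanged, and it loosens if resting function improves. The proposed analysis does not alter it.

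Finally, one might want to replace peak WMSI by the rest-to-peak change. Step 4 shows that this can lose power, and it would hide any benefit to resting function.

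It also stands that this is a secondary endpoint and that the stated sample size is arithmetically sound.

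**Conclusion.** The point holds in limited form. The protocol itself shows that peak WMSI mixes resting and inducible abnormality, that patients with old infarcts are eligible, that resting WMSI has no analytic role, and that the named test does not compare the arms.

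The size of the gain rests on assumed values. With a resting share of 30-50% of the variance, most of the improvement over 81% power comes from pre-treatment peak. Resting WMSI typically adds about 0 to 3 points (3.5 in one setting tabulated), and up to about 8 if inducible ischemia before and after treatment is uncorrelated. The case for using it is clearer interpretation and a small gain in precision at no measurement cost. The ceiling calculation is a caution for reading the result and does not show that the target is wrong.

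**What to change.** In the Statistical plan of WP0:

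- Compare heparin with placebo by ANCOVA on post-treatment peak WMSI, with pre-treatment peak WMSI and pre-treatment resting WMSI as covariates.
- Keep peak WMSI as the ranked secondary endpoint, so that any improvement in resting function is still credited.
- Report the rest-to-peak change in WMSI, compared between arms, as supportive only, and say that it carries extra reading error.
- State the expected mean and SD of resting WMSI, and justify 0.2 against the part of the peak score that is inducible.

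The cost is a few lines of text and one degree of freedom per covariate. Both WMSI values are already calculated, so no new measurement is needed.
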